2. STUDY DESIGN

We will conduct an incomplete cluster randomised stepped wedge trial including 32 general practices. Clusters (units of a general practitioner and his/her practice nurse) will be randomly allocated to four sequential steps over a 22-month period to implement TACTIC (Figure 1). Clusters will be randomised to time points at which they will receive the intervention. To minimize patient burden, data collection is not continuous, but undertaken on a selective number of occasions, which causes an “incomplete” stepped wedge design (14). Recruitment of clusters will start in September 2022, follow-up of the first step will start in March 2023. Follow-up of the last step will end in December 2024.

[figure not shown]

Fig. 1. Incomplete stepped wedge study design; rows are steps to which clusters will be randomised; columns are time periods of each 5 months.

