3. STUDY POPULATION

3.1 Setting and population

This study will be conducted in the primary care cooperative 'Onze Huisartsen BV Arnhem'. This primary care cooperative serves around general practices with > 360,00 registered patients of whom approximately 4,000 patients use antipsychotics. Based on our pilot study we know that around 80 practices are sufficiently equipped to participate in our trial, i.e. they use the General Practice Information Systems Medicom or Promedico ASP and VIPlive, which are necessary for requesting digital consultations with the psychiatrist. A cluster is defined as a duo (or unit) of a general practitioner with his or her practice nurse. As a result, large general practices may provide multiple clusters when consisting of multiple duos.

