3.4 Sample size calculation

The sample size calculation is based on the following findings and expectations. Our pilot showed a reduction of the mean QRISK3 score of 1.9 points. This was after a follow-up period of 3 months, and under suboptimal intervention conditions, e.g. unclear expectation management, modified information meeting due to the corona pandemic. The standard deviation of the difference of QRISK3 score was 3.4 and the standard deviation of a single measurement was 12. This means there is a high reliability on patient level.

$$r_s = 1 - \frac{(SD_{diff}/SD)^2}{2} \approx 0.95$$

We expect that in the trial, after optimisation of the TACTIC procedures, we will be able to detect a reduction of a clinically relevant mean QRISK3 score of 2.5 points in the intervention group, compared to the control condition. Given an SD of 12, an intraclass correlation (ICC) of 0.10, and an α of 0.05, 500 simulated trials indicate that 32 general practices with each 12 patients are needed to provide a power of at least 80%. Given drop-out rates of 20% observed in our pilot study and less than 10% in a UK primary care study evaluating a comparable intervention (15), we include 15 patients per cluster. The required total number of participants will be 480 patients in 32 (or more) clusters.

This calculated sample size has also enough power to detect a clinically relevant improvement of 5 points on de mental health inventory, the mental domain of the SF36, which will be our second primary outcome.

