The MHI-5 consists of five questions with each six answer categories: continuously-mostly-often-sometimes-rarely-never. The answers of the positively formulated questions (questions 3 and 5) will be assigned the values 5, 4, 3, 2, 1, and 0, respectively. The

answers of the negatively formulated questions (questions 1, 2, and 4) will be assigned the values 0, 1, 2, 3, 4, and 5, respectively. Subsequently, a sum score will be calculated, multiplied by 4, resulting in an MHI-5 score ranging from 0 to 100, where a score of 100 equals perfect mental health.

Data analysis will be performed according to the intention-to-treat principle. Data from patients who discontinued follow-up will be included in the analysis up to the point of dropout. Descriptive analyses will be performed to describe the patient characteristics. Mean and standard deviation (std) or median and interquartile range for continuous characteristics and number and percentages for categorical characteristics will be determined. The relationship between treatment and outcome measures measured at 5, 10, 15, and 20 month follow up will be analysed with mixed three level linear or logistic regression, taking into account that the times of measurement are clustered within patients, and patients within general practices. We will perform a model with a random intercept and all other variables fixed. To test the effect of the intervention a model with time, group (intervention or control) and the interaction between time and group will be performed. A value of $p < 0.05$ will be considered statistically significant for all analyses, based on two-sided testing. Analyses will be performed using the Statistical Package for Social Sciences (SPSS, IBM Corp., Armonk, NY) version 25.

We will present QRISK3 scores and MHI-5 scores as means (SDs) for every measurement point, with notification of the number of patients included in the calculation.

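### The primary model allows random intercepts only, so any period-to-period drift of a cluster makes the QRISK3 standard error too small

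*Protocol*

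**What the plan says.** Protocol section 7.1 analyses both primary outcomes with a mixed three-level regression in which "the times of measurement are clustered within patients, and patients within general practices". It then closes the random part: "We will perform a model with a random intercept and all other variables fixed". I read this in the plan's favour, as an intercept for patient and another for practice. The fixed part is "a model with time, group (intervention or control) and the interaction between time and group will be performed". No cluster-by-period effect, random slope, decaying correlation or robust variance is named.

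Section 3.4 supplies the variance figures: "Given an SD of 12, an intraclass correlation (ICC) of 0.10", and "The standard deviation of the difference of QRISK3 score was 3.4". It gives no correlation between periods within a cluster.

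The randomised unit is the duo: "Clusters (units of a general practitioner and his/her practice nurse) will be randomly allocated to four sequential steps" (section 2). Section 3.1 adds that "large general practices may provide multiple clusters when consisting of multiple duos". The top level of the model is nevertheless the general practice.

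**The concern.** In a stepped wedge, exposure is set by cluster and period. Random intercepts absorb what is constant in a cluster or patient, and fixed time effects absorb what is common to all clusters. Neither absorbs a deviation that one cluster's patients share in one period, such as a change in measurement practice, data capture or local treatment habits. That deviation adds to the error of the treatment estimate, but an intercept-only model spreads it over the patients as independent noise. The confidence interval is then too narrow and the 5% level is exceeded. The more precise the individual measurement, the less drift is needed, and QRISK3 as described in section 3.4 is very stable within patients.

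A smaller, separate point is the level of the model. Where one practice supplies several duos, the randomised unit and its period variation have no term. Leaving out a time-constant duo intercept does not by itself shrink the standard error.

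**Working it through.** **Inputs.** From section 3.4: total variance 12² = 144; cluster variance 0.10 × 144 = 14.4; within-patient variance 3.4²/2 = 5.78; hence patient variance 144 − 14.4 − 5.78 = 123.82; 32 clusters of 12; effect 2.5 points. From sections 2 and 5.3: four steps and measurements at 0, 5, 10, 15 and 20 months. Assumed: 8 clusters per step, all cells observed (Figure 1 is not available), a constant effect, and the CAC.

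**1. The plan's own figures.** 12/(1 − 0.20) = 15 and 15 × 32 = 480, as stated. For power, let σ² be the part of a cluster-period mean that is independent between periods and τ² the part that is constant. With I = 32 and T = 5,

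Var = Iσ²(σ² + Tτ²) / [(IU − W)σ² + (U² + ITU − TW − IV)τ²].

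U = 80 is the number of exposed cluster-periods. W = 8² + 16² + 24² + 32² = 1,920 sums the squared numbers of exposed clusters over periods. V = 8(16 + 9 + 4 + 1) = 240 sums the squared numbers of exposed periods over clusters. The two brackets are 640 and 1,920.

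- Ignoring within-patient correlation: σ² = 129.6/12 = 10.8 and τ² = 14.4. Var = 345.6 × 82.8/34,560 = 0.828, SE 0.910, power Φ(2.5/0.910 − 1.96) = 78%, close to the planned 80%.
- With the protocol's within-patient variance: σ² = 5.78/12 = 0.482 and τ² = 14.4 + 123.82/12 = 24.72. SE 0.200, power above 99.9%. This is the SE that the planned model reports.

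**2. Adding drift.** A CAC below 1 moves v = 14.4(1 − CAC) from the constant cluster part to a cluster-by-period part. Holding the within-patient variance at 5.78, the true period-specific variance of a cluster mean is v + (5.78 − v)/12, but the model uses 5.78/12. The ratio is

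1 + 11v/5.78,

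the usual design effect, with v/5.78 as the share of within-patient variance common to a cluster-period. Because τ² is so much larger than σ², the estimate rests almost entirely on within-cluster comparisons, so the square root of this ratio is very nearly the factor by which the SE is too small.

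At CAC 0.95: v = 0.72; 1 + 11 × 0.72/5.78 = 2.37; √2.37 = 1.54; true SE 0.308; type I error 2[1 − Φ(1.96/1.54)] = 20%.

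The full calculation (generalised least squares for the planned model, sandwich variance under the true one) gives:

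| CAC (assumed) | Drift SD (points) | Shared share | Model SE | True SE | Two-sided type I | False benefit |
|---|---|---|---|---|---|---|
| 1 | 0 | 0% | 0.200 | 0.200 | 5% | 2.5% |
| 0.99 | 0.38 | 2% | 0.200 | 0.226 | 8% | 4% |
| 0.98 | 0.54 | 5% | 0.200 | 0.249 | 11.5% | 6% |
| 0.95 | 0.85 | 12% | 0.200 | 0.308 | 20% | 10% |
| 0.90 | 1.2 | 25% | 0.200 | 0.387 | 31% | 16% |
| 0.80 | 1.7 | 50% | 0.200 | 0.509 | 44% | 22% |

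**3. Simulation.** Fitting the planned model by REML to 500 simulated trials per setting rejected in 4.6%, 22%, 31% and 46% at CAC 1, 0.95, 0.90 and 0.80.

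**4. The time-by-group term.** With a linear interaction, the group and interaction coefficients are each understated by the same factor (1.54 at CAC 0.95). If the test is a joint one of all group terms, which section 7.1 does not say, type I error at CAC 0.95 is 28% with linear time and 35% with categorical time.

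**5. Sensitivity at CAC 0.95 (base 20%).**
- SD of difference 5: 12.5%; 6: 10%.
- ICC 0.05: 13%; 0.02: 8%.
- Drift added on top of 5.78 instead of taken from it: 19%.
- 15 patients per cluster: about 24%.
- Four assumed incomplete layouts: within 0.5 points of the complete one.
- MHI-5 with assumed SD 20, ICC 0.05 and within-patient correlation 0.6: 5.8% (8% at CAC 0.80).

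**The case against.** The strongest reply is that the harm depends on a number the protocol does not contain, and that the protocol gives reasons to expect a CAC near 1. The same patients are followed. Section 7.1 freezes age at baseline, sets several chronic conditions constant over time, back-fills blood pressure treatment started because of the intervention, and carries forward missing blood pressure and BMI. All clusters work in one cooperative with one regional programme, so programme-wide change falls into the fixed time effect. The SD of 3.4 comes from a small pilot with 3 months of follow-up, and a larger SD weakens the result. Variance estimators and sensitivity analyses are also commonly left to an analysis plan.

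Part of this stands. The size is conditional, the 0.80 and 0.90 rows describe substantial drift (and 44% becomes about 36% at 0.80 if drift is added to the 5.78), and the damage is confined to a null or small QRISK3 effect.

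It does not remove the point. Blood pressure, lipids, weight and smoking still vary over time and are recorded at routine practice visits. Section 7.1 fills a missing cholesterol ratio or smoking status with a set value, so I infer that poor data capture in one period would move several patients of a cluster together. A drift SD of 0.5 points, one fifth of the target effect, already gives 1 + 11 × 0.25/5.78 = 1.48 and a type I error of 10.7%. Nor is this a gap left for later: section 7.1 states the random part, and an analysis plan that added the term would depart from it.

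**Conclusion.** The concern holds and should be fixed before analysis. The planned model is valid only if clusters do not drift at all. On the protocol's own variance figures, type I error for QRISK3 rises to about 8% at CAC 0.99, 20% at 0.95 and 44% at 0.80, with the interval too narrow by factors of 1.13, 1.54 and 2.54. The direction is certain whenever drift exists; the size rests on the assumed CAC and on the pilot SD of 3.4, so confidence in the magnitude is medium. It does not depend materially on the missing Figure 1. The issue is one of error rate and interval width, not power, and it matters little for MHI-5. The mismatch between practice and duo is real but secondary.

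**What to change.** In section 7.1, replace the random-intercept sentence with: random intercepts for patient and for the randomised cluster (GP-nurse duo), with general practice as a further level where it supplies more than one duo, plus a random duo-by-period effect. Name a small-sample method for the degrees of freedom, given 32 clusters. If many practices supply several duos, say whether a practice-by-period term is also fitted, since such duos may drift together. In section 3.4, state an assumed CAC with a range.

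The cost is one or two extra variance terms, with no added patients or visits. If the period variance is estimated at zero, the period term drops out and random intercepts alone remain. If drift exists, the interval widens as it should: at CAC 0.95 in a complete layout the half-width is 2.05 × 0.307 = 0.63 points (t, 27 df) instead of 1.96 × 0.200 = 0.39. Power for 2.5 points under the corrected model is at least 99% for CAC 0.90 or higher in the complete and all four incomplete layouts tried. At CAC 0.80 it is 94% (sparsest layout) to 99.6% (complete), still above the planned 80%.

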on antipsychotic use, and the QRISK3 score at baseline (see Methods 6.1.2. Secondary study parameters).

During the multidisciplinary meeting, the participating patient (and carer), the general practitioner, a psychiatrist, the primary care nurse, and if desired an experience expert (patient coach who lived the experience) will review the patient's antipsychotic use and all other relevant medication (if applicable). Also, possible cardiovascular risk factors will be addressed, such as smoking status, blood pressure, Body Mass Index, blood glucose and cholesterol levels. The multidisciplinary meeting will result in a set of individualised treatment suggestions, including advice on antipsychotic use (e.g. continuation, deprescribing, or switching) and reducing cardiovascular risk.

Step 3: A week after the multidisciplinary meeting, the patient has a consultation with the general practitioner during which the set of individualised treatment suggestions will be translated into an action plan through shared-decision making. This shared-decision making process will benefit the adherence and outcome of the plan. The plan will also define the tasks and responsibilities of the various healthcare providers. Potential actions are altering antipsychotic use, initiating antihypertensive medication or statins, referral to the chronic care nurse (in Dutch: POH-S) for example for smoking cessation, referral to the primary care mental health nurse (in Dutch: POH-GGZ), the dietician, the physical therapist, or a life style coach.

The effects of TACTIC in addition to usual care will be compared to usual care alone, in which patients will be their own comparator, prior to treatment initiation.

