After signed informed consent and inclusion, baseline measurement will take place and patients will fill in a digital questionnaire using Castor EDC, containing MHI-5, EQ-5D-5L, TIC-P and LUNSERS. As part of the preparation for the multidisciplinary meeting, patients will be asked to fill in a custom-made questionnaire on antipsychotic use. This questionnaire will help healthcare professionals prepare for the meeting and will give the patient insight in possible topics that can be addressed during the meeting. In case patients do not have an email address, we will send the questionnaires by mail. Patients will then watch the information video at home, attend the multidisciplinary meeting, and attend a consultation with their general practitioner, as described in section 5. At five months follow-up, patients will be invited for follow-up (monitoring) measurements at the general practice as part of the regular regional cardiovascular risk management programme (usual care), to undergo physical examination (measuring weight and blood pressure), venapuncture and urinalysis (for measuring risk factors, i.e. HbA1c, blood glucose, lipid spectrum and kidney function). As part of the evaluation, patients will also fill in questionnaires, containing MHI-5, EQ-5D-5L, LUNSERS, TIC-P and general questions about smoking status and family history of coronary heart disease. Depending on which step the cluster has started, patients will undergo one to four follow-up measurements, every five months. This is in line with the routine check-ups patients will have in the regular cardiovascular risk management programme. During the last follow-up measurement, they are also asked to fill in the CSQ-8. Table 1 presents the schedule of assessments.

No diagnostic procedures or treatment will be postponed.

	Visit general practice	Digital information	Physical examination	Laboratory tests	Questionnaires
Week 1 Routine screening and inclusion after informed consent	X		X	X	
Week 2 Baseline measurement					X
Week 3 Information video		X			
Week 4/5	X				

Multidisciplinary meeting					
Week 5/6 Consultation with GP	X				
Month 5 Routine consultation as part of usual care. Follow-up measurement 1 Start Step 2 at Week 1	X		X	X	X
Month 10 Routine consultation as part of usual care. Follow-up measurement 2 Start Step 3 at Week 1	X		X	X	X
Month 15 Routine consultation as part of usual care. Follow-up measurement 3 Start Step 4 at Week 1	X		X	X	X

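### The only stated test of the intervention effect is a time-by-group interaction model, although the stepped wedge is sized on one average intervention-versus-control contrast

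*Protocol*

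**What the plan says.** Section 2 describes an incomplete stepped wedge with four steps: "Clusters will be randomised to time points at which they will receive the intervention". Section 4 makes the comparison partly within patients: "patients will be their own comparator, prior to treatment initiation". In Table 1 (section 5.3) the steps begin at months 0, 5, 10 and 15; the month 15 row reads "Start Step 4 at Week 1", and follow-up of all clusters ends at month 20.

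Section 3.4 sizes the trial on "a reduction of a clinically relevant mean QRISK3 score of 2.5 points in the intervention group, compared to the control condition", with SD 12, ICC 0.10, alpha 0.05 and 32 practices of 12 patients for at least 80% power. It adds that the same sample suffices for a "clinically relevant improvement of 5 points on de mental health inventory".

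Section 7.1 states that "outcome measures measured at 5, 10, 15, and 20 month follow up will be analysed with mixed three level linear" or logistic regression, with a random intercept and all other terms fixed. The intervention effect is tested by "a model with time, group (intervention or control) and the interaction between time and group will be performed". A p-value below 0.05 "will be considered statistically significant for all analyses, based on two-sided testing". The protocol does not say which term decides, whether time is linear or categorical, where its origin lies, or whether it means calendar time or time since TACTIC.

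**The concern.** In a parallel trial with a baseline, the time-by-group interaction is often the treatment effect, because the groups start equal and diverge. In a stepped wedge every cluster crosses over, so group must be a time-varying indicator. The effect of being treated is then carried by the group term, and the interaction asks only whether that effect changes over calendar time. A reader who follows section 7.1 in the usual way could take the interaction p-value as primary and so test something other than the effect the trial was sized for.

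Reading the group term instead does not settle the matter. Beside an interaction, the group coefficient is the effect at the time coded zero. If that is month 0, it is the effect at a moment when no cluster has had TACTIC. The same data and the same stated model can therefore give different primary p-values, for both primary outcomes.

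**Working it through.** **Inputs.** From section 3.4: effect 2.5, SD 12 (variance 144), ICC 0.10, 32 clusters of m = 12, SD of the within-patient difference 3.4. From Table 1: step starts at months 0, 5, 10 and 15. Assumed: 8 clusters per step, and the measurement layout, because Figure 1 is not shown. Three layouts were tried: (F) all steps measured at months 0, 5, 10, 15 and 20; (S) staggered entry, with a baseline at the step's own start and then 4, 3, 2 or 1 follow-ups; (U) only months 5 to 20, all steps measured.

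**Within-patient correlation.** The protocol's formula gives r = 1 − (3.4/12)²/2 = 1 − 0.0803/2 = 0.96 (printed as about 0.95).

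**Method.** Generalised least squares on cluster-period means. The covariance within a cluster is (σc² + σp²/m)J + (σe²/m)I, with σc² = 0.10 × 144 = 14.4, σp² = (r − 0.10) × 144 and σe² = (1 − r) × 144. Here J is the all-ones matrix and I the identity. Var(β) = (Σ 8 Xₛ′V⁻¹Xₛ)⁻¹ over the four steps. Power = Φ(2.5/SE − 1.96). With no extra patient correlation r = 0.10, so σp² = 0.

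**Step 1: the plan's own figure.** One treatment coefficient adjusted for period, layout F, r = 0.10: SE 0.91, and Φ(2.5/0.91 − 1.96) = 78%. The Monte Carlo standard error of the protocol's 500 simulations is √(0.8 × 0.2/500) = 1.8 points, so this agrees with 80%. It fits a trial sized on an average contrast.

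**Step 2: the stated model under a constant effect of 2.5 points, linear time, r = 0.10.**

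| Deciding term | F | S | U |
|---|---|---|---|
| Interaction | 5% | 5% | 5% |
| Group, time from month 0 | SE 1.40, 43% | SE 1.53, 37% | SE 1.81, 28% |
| Group, time centred at month 10 | SE 0.91, 78% | SE 0.97, 73% | SE 0.97, 73% |
| Joint 2-df test | 69% | 64% | 64% |
| For comparison: single period-adjusted coefficient | SE 0.91, 78% | SE 1.00, 71% | SE 0.97, 73% |

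The interaction row needs no variance assumption: with a constant effect its expectation is 0, so it rejects at alpha. In 5,000 simulated trials per setting (three layouts, with and without the high correlation) it rejected 4.6% to 5.3% of the time.

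**Step 3: the same at r = 0.96.** In F / S, the month-0 group term has SE 0.30 / 0.32, the centred group term 0.20 / 0.22 and the single coefficient 0.20 / 0.22. Power is about 100% for every reading except the interaction, which stays at 5%.

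**Step 4: meaning of the group term.** Illustration: the effect is −2.5 at month 10 and grows by 1.25 per 5-month calendar period. The month-0 group term then targets −2.5 + 2 × 1.25 = 0, at any correlation. Here the interaction does have power: 66% / 47% (F / S) at r = 0.10 and about 100% at 0.96.

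**Step 5: a check on the remedy.** Suppose the effect is −1.25 per 5-month period since TACTIC start. Over the ten treated step-periods the exposure times sum to (1+2+3+4) + (1+2+3) + (1+2) + 1 = 20, so the average effect is −1.25 × 20/10 = −2.5. The single coefficient then has expectation −0.88 / −0.63 (F / S) at r = 0.10, and −0.63 / −0.02 at 0.96.

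**The case against.** The strongest reply is that the deciding contrast and the coding of time are details that a protocol commonly leaves to a statistical analysis plan, which may exist. Section 7.1 fixes the levels, the random intercept, the two-sided 5% level and the intention-to-treat principle, and a centred group term or a joint test from the stated model would be valid. This stands for the coding of time. It does not dispose of the point, because the protocol is not silent: it names an interaction model as the test of effect, and a plan faithful to that sentence could make the interaction primary.

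Three further objections stand and limit the point.

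- A reader might infer from the 43%, 37% and 28% in the table that the trial is too small. Those figures assume no extra within-patient correlation, whereas section 3.4 reports about 0.95 and section 7.1 models patients as a level. At that value the loss for QRISK3 disappears. For MHI-5 the protocol gives no SD or correlation, so nothing can be computed either way.
- A reader might infer that the interaction test fails whatever happens. It fails for a constant effect; for an effect that changes over calendar time it can have good power. Nor does section 7.1 say that the interaction alone decides.
- A single constant coefficient is not a neutral repair. Step 5 shows that it can miss most of an effect that builds up after a one-time intervention.

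With categorical time, the effects at months 0 and 20 cannot be estimated (no treated records at month 0, no control records at month 20). That is a feature of a wedge in which every cluster crosses over, and not a defect in itself.

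**Conclusion.** The point holds in limited form and should be fixed before analysis. The stated test does not determine the primary p-value, and its interaction term does not test the effect used for sizing. The 5% detection rate for a constant effect applies to both primary outcomes and does not depend on layout, SD or correlation. It does assume that group is a time-varying indicator and that the time trend is correctly specified. The dependence of the group term's meaning on the time origin is equally firm whenever the effect varies over calendar time. All other SEs and powers rest on assumed layouts, and those at r = 0.10 are not evidence of a shortfall for QRISK3. The documents do not support a claim that 480 patients are too few.

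**What to change.** Replace the sentence on the test in section 7.1 (or settle it in the analysis plan before data are analysed) along these lines: *The primary test, for QRISK3 and for MHI-5, is the coefficient of one time-varying treatment indicator (0 before, 1 after the cluster's TACTIC start) in the three-level mixed model, with measurement period as a categorical fixed effect. The time-by-group interaction is secondary.*

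Add a prespecified sensitivity analysis in which the effect may differ by time since TACTIC start, and report the average effect over exposure time.

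The cost is a few sentences and a few lines of model syntax, with no extra data or patients. The downside should be stated openly: the primary coefficient assumes a constant effect and can be biased if the effect grows or fades after TACTIC, while the exposure-time analysis is less precise. How much less depends on the layout in Figure 1, so its expected precision should be worked out for that layout before it is relied on.
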